This is a single-center, Phase 2, single-blind, 4-period sequential study will obtain a preliminary assessment of the effects of ergoloid mesylates (EM) 1 mg TID and 5-hydroxytryptophan (5-HTP) 100 mg TID and the combination compared to a placebo period in participants with Fragile X Syndrome. The study will consist of a Screening period of up to 28 days prior to initial study drug administration, followed by four 4 week single-blind treatment periods. The screening and baseline visits may occur at the same time, provided the results of safety labs can be obtained. A final follow-up visit or phone contact for safety is planned one week after the conclusion of Period 4.

Eligible participants will be started on EM for 4 weeks in Period 1, then will take EM and 5-HTP for 4 weeks in Period 2, then, 5-HTP for 4 weeks in Period 3, then placebo for 4 weeks in Period 4. Study visits will occur at baseline and every 4 weeks at transition times between periods, then at the end of the study.

Brief cognitive and behavioral assessments will be performed during each clinic visit. Safety and tolerability assessments will include adverse event monitoring, vital signs, blood chemistry and hematology, and urinalysis.

	4 Weeks Period 1	4 Weeks Period 2	4 Weeks Period 3	4 Weeks Period 4		
Screen/Enroll ───→	EM	EM + 5-HTP	5-HTP	Placebo		
N=15 participants						
EM=ergoloid mesylates 1 mg TID, 5-HTP = 5-hydroxytryptophan 100 mg TID						
Planned Numbers of Participants						
Enrollment of a total of 15 eligible participants is planned.						
Study Duration						
The total duration of the study for each participant will be up to 21 weeks, including a maximum of 4-week screening						

The total duration of the study for each participant will be up to 21 weeks, including a maximum of 4-week screening period, four 4-week Single-Blind treatment Periods, and a follow-up telephone call approximately 1 week after the last treatment visit.

Study Procedures:

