Participants will return to the clinic at the end of each Period at weeks 4, 8, 12, and 16. Cognitive and behavioral evaluations will be repeated at Weeks 4, 8, 12, and 16 (end of Period 1, 2, 3, 4). Additionally, participants will be monitored for adverse events via a telephone call at the end of Week 1 of each Period, and one week following completion of Period 4 or following early discontinuation. During clinic visits, adverse effects will be assessed, and laboratory measures and vital signs will be repeated according to the Schedule of Assessments. Suicidality risk will also be evaluated during the treatment periods per the Schedule of Assessments; if a concern is detected, the participant will be referred for further evaluation and treatment.

Participant Inclusion/Exclusion Criteria:

Individuals are eligible for the study if they meet all of the Inclusion and none of the Exclusion criteria. The criteria below will be assessed during Screening, which will be up to 28 days prior to first study drug administration. Continued participant eligibility will be verified on Baseline Day 1.

Participant Inclusion Criteria

- 1. Male aged 18 to 45 years, inclusive.
- 2. Participant has Fragile X Syndrome with a molecular genetic confirmation of the full Fragile X Mental Retardation (FMR1) mutation (≥200 CGG repeats).
- 3. Current treatment with no more than 3 prescribed psychotropic medications. Anti-epileptic medications are permitted and are not counted as psychotropic medications if they are used for treatment of seizures. Anti-epileptics for other indications, such as the treatment of mood disorders, count towards the limit of permitted medications.
- 4. Permitted concomitant psychotropic medications must be at a stable dose and dosing regimen for at least 2 weeks prior to Screening and must remain stable during the period between Screening and the commencement of study medication.
- 5. Anti-epileptic medications must be at a stable dose and dosing regimen for 12 weeks prior to Screening and must remain stable during the period between Screening and the commencement of study medication.
- 6. Participants with a history of seizure disorder who are currently receiving treatment with anti-epileptics must have been seizure-free for 3 months preceding screening, or must be seizure-free for 3 years if not currently receiving anti-epileptics.

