- Clinical Global Impression Improvement Investigator rated (CGI-I): Standardized ranking scale with 7 rankings
- Visual Analog Scale (VAS) Parent/caregiver-rated assessment of participant-specific behavioral anchors: Domains of daily functioning, anxiety/irritability and language.
- ABC: Parent/caregiver-rated scale with six subscales to assess irritability, social avoidance, lethargy, hyperactivity, inappropriate speech and social avoidance, using ABC-FX factoring system.
- ADAMS: Parent/caregiver rated scale with a total score and five sub-scores to assess manic/hyperactive behavior, depressed mood, social avoidance, general anxiety, and obsessive/compulsive behavior.
- Vineland-3 Adaptive Behavior Scale: Clinician-administered standardized interview yielding adaptive behavior composite score and domain standard scores in domains of: communication (receptive, expressive, and written adaptive language functions), daily living skills (personal, domestic, and community skills), socialization (interpersonal relationships, play and leisure time, and coping abilities), and motor skills (gross and fine motor skills).
- Event-Related Potentials (ERP) Measure of auditory habituation based on EEG signals
- Eye Tracking Measure of gaze aversion (social anxiety) and pupilometry (autonomic function)

Safety and Tolerability: The safety variables to be assessed include adverse events; clinical laboratory parameters (chemistry, hematology, and urinalysis); physical examinations; and vital signs (including blood pressure, heart rate, and respiratory rate).

Statistical Considerations

Efficacy Analyses

The primary efficacy population will be the intent to treat (ITT) efficacy population, which will include all participants who received at least one dose of treatment and returned for at least one follow-up visit. The completers population (CP), defined as all randomized participants who complete all 4 treatment periods with no significant protocol violations, will be used to evaluate the robustness of the ITT results.

All efficacy parameters will be summarized at each time point collected and standard descriptive statistics provided. Baseline measurements are defined as those obtained on Day 1/Period 1 prior to receipt of any study medication. For cognitive parameters measured at baseline, change from baseline will also be calculated and standard descriptive statistics provided for each time point.

Safety Analyses

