3.2 Rationale

FXS is a disorder in which affected individuals display intellectual disability as well as symptoms typical of autism spectrum disorder, due to silencing of the X-linked, *FMR1* gene.

Two previously untested products in FXS were predicted *in silico* to have beneficial activity in FXS and proposed for *in vivo* follow-up in *Fmr1* KO mice, namely ergoloid mesylates (EM) and 5-hydroxytryptophan (5-HTP). Both agents showed an interesting polypharmacological predicted bioactivity spectrum, which is a necessity for complex disorders, such as FXS. The most strongly associated targets after the statistical enrichment were HTR1A, HTR2A, DRD2 and OPRM1 for EM, and ESR1, HTR1A, GRIA1, and GRIK1 for 5-HTP. Both products worked in the majority of tests *in vivo* in the *Fmr1* KO mouse model (see below Section 3.3.1 Preclinical Pharmacology), which led to the hypothesis that their serotonergic action would be additive, whilst the diversity in target and pathway modulation could indeed produce some synergistic effect, which was also confirmed *in vivo*, leading to the alleviation of all FXS phenotypes in the *Fmr1* KO mouse.

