4 INVESTIGATIONAL PLAN

4.1 Overall Study Design

This is a single center, Phase 2, single-blind, 4 period study to obtain preliminary assessment of the effects of ergoloid mesylates (EM), 5-hydroxytryptophan (5-HTP), and the combination in participants with Fragile X Syndrome. As schematic display of the study design is shown in Figure 7.

The study will consist of a Screening period of up to 28 days prior to initial study drug administration, followed by four 4-week single-blind treatment periods. The screening and baseline visits may occur at the same time, provided the results of safety labs can be obtained. No washout period will be utilized between treatment periods. A final follow-up phone contact for safety is planned one week after the conclusion of Period 4.

Eligible participants will be started on over-encapsulated EM 1 mg TID during Period 1, then will take EM 1 mg TID and 5-HTP 100 mg TID in Period 2, then 5-HTP 100 mg TID in Period 3, and placebo in Period 4. Throughout all 4 periods, participants will take two identical capsules three times a day. If only taking one over-encapsulated drug, they will take one over-encapsulated placebo pill with the drug at each dose, and when in period 4 they will take two over-encapsulated placebo pills at each dose.

Cognitive and behavioral assessments will be performed during each clinic visit. Safety and tolerability assessments throughout the study will include adverse event monitoring, vital signs, blood chemistry, hematology, and urinalysis.

Figure 7 Study Design Schematic

N=15 participants

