10.4 Efficacy: Cognitive, Behavioral and Pharmocodynamic Measures Analysis

All cognitive and behavioral parameters will be summarized at each time point collected and standard descriptive statistics provided. Baseline measurements are defined as those obtained on Day 1/Period 1 prior to receipt of any study medication. For cognitive parameters measured at baseline, change from baseline will also be calculated and standard descriptive statistics provided for each time point.

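### The four periods form a within-participant 2×2 factorial, but section 10.4 plans only per-visit summaries; the three factorial contrasts should be added as supplementary estimates with intervals and stated limits

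*Combined protocol and SAP*

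**What the plan says.** Section 4.1 fixes the order. EM alone comes first, and the sentence goes on: "then will take EM 1 mg TID and 5-HTP 100 mg TID in Period 2, then 5-HTP 100 mg TID in Period 3, and placebo", with placebo the last of the four. The synopsis agrees: "Eligible participants will be started on EM for 4 weeks in Period 1, then will take EM and 5-HTP for 4 weeks in Period 2", followed by "5-HTP for 4 weeks in Period 3, then placebo for 4 weeks in Period 4". Assessments are equally spaced: "Participants will return to the clinic at the end of each Period at weeks 4, 8, 12, and 16". Section 4.1 provides no washout.

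The synopsis describes the study as setting the active regimens against a placebo period. Section 3.2 describes the mouse results, "which led to the hypothesis that their serotonergic action would be additive", and goes on to expect some synergy.

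For efficacy, section 10.4 plans: "All cognitive and behavioral parameters will be summarized at each time point collected and standard descriptive statistics provided". It adds: "For cognitive parameters measured at baseline, change from baseline will also be calculated and standard descriptive statistics provided for each time point". The synopsis has the parallel sentence: "All efficacy parameters will be summarized at each time point collected and standard descriptive statistics provided". Neither place defines a between-period difference, a factorial effect, a model or an interval. Section 10.1 gives no sample-size calculation; planned enrolment is 15, and section 5.5 says that withdrawals are not replaced.

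**The concern.** EM yes/no crossed with 5-HTP yes/no gives four cells, and each participant passes through each cell once. Whether two drugs add or act synergistically is a factorial question, yet the plan handles the cells as four unrelated visits.

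Two things are lost. First, precision: the SD of a within-participant contrast depends on how a participant's visits correlate, and per-visit means and SDs do not show that. A reader could work out point estimates from the visit means but could not attach an interval. Second, labelling: with a fixed order, every between-regimen comparison mixes treatment with time to some degree, and the degree differs greatly between comparisons. The planned output does not tell the reader which comparisons a steady drift (practice, fading expectancy, season) affects most and which it spares.

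**Working it through.** **Inputs.** Period order and equal 4-week spacing (synopsis, section 4.1); n = 15 (synopsis). The documents give no SD, alpha or effect size, so results are in units of s, the within-participant error SD, and two-sided 95% intervals are assumed. There is no figure in the plan to reproduce.

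**Setup.** Let y1 to y4 be the scores at weeks 4, 8, 12 and 16 (EM, EM + 5-HTP, 5-HTP, placebo), and d the non-treatment change per period. A contrast with weights w has drift bias d·Σ(w·t) for t = 1 to 4. With exchangeable errors its variance per participant is s²·Σw².

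| Estimate | Weights at wk 4, 8, 12, 16 | Linear drift | Variance (s²) |
|---|---|---|---|
| 5-HTP main effect | −½, +½, +½, −½ | (−1+2+3−4)/2 = 0 | 1 |
| EM main effect | +½, +½, −½, −½ | (1+2−3−4)/2 = −2d | 1 |
| Interaction | −1, +1, −1, +1 | −1+2−3+4 = +2d | 4 |
| EM − placebo | +1, 0, 0, −1 | 1−4 = −3d | 2 |
| Combination − placebo | 0, +1, 0, −1 | 2−4 = −2d | 2 |
| 5-HTP − placebo | 0, 0, +1, −1 | 3−4 = −1d | 2 |

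Any difference between two distinct visits has a non-zero drift term. So among factorial effects and two-visit differences over the four periods, only the 5-HTP main effect has none.

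**Precision at n = 15.** t(14, 0.975) = 2.145.
- 5-HTP main effect: 2.145 × √(1/15) = 0.55s.
- Two-visit difference: 2.145 × √(2/15) = 0.78s.
- Interaction: 2.145 × √(4/15) = 1.11s.

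**When the variance ratio of one half changes.**
- If participants differ in treatment response with variance r·s², the ratio is (1 + r)/(2 + r): 0.60, 0.67 and 0.75 for r = 0.5, 1 and 2.
- Under AR(1) errors with correlation 0.5, the 5-HTP main effect has variance 0.5625, against 1.00, 1.50 and 1.75 for differences one, two and three periods apart.

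**What enters the 5-HTP contrast.**
- *Interaction.* If 5-HTP alone has effect h and the interaction is I, then y3 − y4 gives h and y2 − y1 gives h + I. The average is h + I/2.
- *Curvature.* The weights −, +, +, − are the quadratic time contrast, so curvature is fully aliased with 5-HTP. On an illustrative plateauing practice curve with cumulative gains 1, 1.5, 1.75, 1.875, the bias is (1.5 + 1.75 − 1 − 1.875)/2 = +0.19 of the first gain. Plain 5-HTP − placebo has 1.75 − 1.875 = −0.125. If gains shrink by a factor x each period, the ratio of the two biases in size is (1 − x²)/(2x²), which exceeds 1 when x < 0.577. Here x = 0.5 gives 0.75/0.5 = 1.5.
- *Carry-over.* A fraction c of the 5-HTP effect persisting into Period 4 shrinks the contrast by c/2 of that effect; a fraction c of the EM effect persisting into Period 3 adds c/2 of the EM effect.
- *Visit windows.* With ±5 days at each visit, one participant could in the worst case retain 4 × ½ × 5 = 10 days of linear drift.

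**Trend-free contrasts that use baseline (y0, t = 0).**
- EM: y1 − (0.75·y0 + 0.25·y4). Drift 1 − 1 = 0; variance 1 + 0.5625 + 0.0625 = 1.625.
- Combination: y2 − (0.5·y0 + 0.5·y4). Drift 2 − 2 = 0; variance 1 + 0.25 + 0.25 = 1.5.
- 5-HTP: y3 − (0.25·y0 + 0.75·y4). Drift 3 − 3 = 0; variance 1.625.

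These absorb part of any placebo response, because baseline precedes all capsules.

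**The case against.** The strongest reply is that the study is exploratory, small and openly descriptive, and that the 5-HTP main effect answers none of the stated objectives directly. Section 3.4.1 asks about EM, 5-HTP and the combination. The contrast averages 5-HTP with and without EM, and under the synergy that section 3.2 expects it would credit half the interaction to 5-HTP. It is also not robust to the most plausible time effect: repeated cognitive testing tends to plateau, and on an early plateau the contrast is further from zero than 5-HTP − placebo and, where higher scores are better, errs in the drug's favour. All of this stands.

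Three stronger readings are tempting, and the documents do not support them:
- *That this is the only trend-free contrast available.* The synopsis makes baseline the common reference, and the baseline-and-placebo combinations above cancel linear drift for each regimen.
- *That it should be the lead efficacy result.* Freedom from linear drift is bought with full exposure to curvature and a different estimand, which is a debatable trade.
- *That it is equivalent to doubling n.* That needs exchangeable errors and no variation between participants in treatment response.

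Two practical objections also stand. A per-participant contrast needs all four visits, whereas the ITT population in section 10.3 needs only one follow-up visit. And there are many outcomes: NIH-TCB 7, KiTAP 4, VAS 3, ABC 6 and ADAMS 6 (five factors and a total) already make 26. Three contrasts each give 78 intervals, of which about 78 × 0.05 = 3.9 would exclude zero by chance if there were neither effect nor trend.

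None of this defends leaving the contrasts out. Labelled estimates with intervals need no hypothesis test or power claim, and per-visit summaries cannot supply them.

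**Conclusion.** The point holds as a cheap improvement to the analysis. The design is a within-participant 2×2 factorial, and the plan gives no precision for any contrast between its cells. Within the four treatment periods, the 5-HTP main effect is the only factorial effect or two-visit difference free of linear drift. Its variance is 0.50 of a two-visit difference under exchangeable errors, and about 0.60 to 0.75 of it if variation in treatment response is 0.5 to 2 times the error variance. The EM main effect and the interaction, which is the synergy question, carry −2d and +2d.

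This rests on equal spacing, equal error variances and drift that is close to linear. It does not make the 5-HTP contrast unbiased, and it does not justify placing it above the planned summaries.

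**What to change.** Add to section 10.4, as supplementary exploratory estimates for each continuous outcome, with 95% intervals:
- the 5-HTP main effect, (Wk8 + Wk12 − Wk4 − Wk16)/2;
- the EM main effect, (Wk4 + Wk8 − Wk12 − Wk16)/2;
- the interaction, Wk8 − Wk4 − Wk12 + Wk16.

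Estimate them from a mixed model with the four regimens as fixed effects and a participant effect, so that ITT participants with missing visits contribute. Period cannot be a separate factor, because each regimen occurs in only one period. As a check, compute the contrasts per participant in completers; this does not rely on the exchangeable-error assumption.

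State with the results that:
- the EM main effect and the interaction are confounded with linear trend (−2d and +2d);
- the 5-HTP contrast is the 5-HTP-alone effect plus half the interaction;
- it is fully aliased with curvature and can be more biased than 5-HTP − placebo when practice plateaus early;
- carry-over affects it, as there is no washout;
- intervals are not adjusted for multiple outcomes.

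The cost is a short paragraph in section 10.4, a little more analysis and more unadjusted intervals to interpret. No new data or visits are needed.

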10.5 Safety Analysis

Safety analysis will be based on all participants receiving at least one dose of study medication. Treatment emergent AEs will be summarized based on the frequency of AEs and their severity for all dosed participants. Adverse Events (AEs), including clinically meaningful laboratory abnormalities and significant behavioral changes, will collected. AE severity and relatedness to treatment will be assessed. AEs will be tabulated for placebo and BPN14770 treatments using preferred terms and system organ classes. Summaries will also be provided by severity and relationship to treatment. Serious Adverse Events (SAEs) will be summarized separately, in a manner similar to that used for Adverse Events.

Overall safety and tolerability will be assessed by clinical and/or statistical review of all safety parameters including adverse experiences, laboratory values, vital signs, physical exams, and ECG data. General clinical and laboratory adverse events will be presented in frequency tables. Summary statistics (n, mean, SD, median, and range (minimum, maximum) will be tabulated for the observed values and the change (or percent change) from baseline for all continuous parameters for vital signs and laboratory tests.

11 DATA MANAGEMENT

11.1 Data Handling

Data will be recorded at the site on CRFs. All corrections or changes made to any study data will be noted on the CRFs and dated appropriately.

11.2 Data Entry into EDC

Data will be collected and processed in RedCap. Data will be recorded in RedCap as the study is in progress. All site personnel must log into the system using their secure user name and password in order to enter, review, or correct study data. All passwords will be strictly confidential.

The Investigator has ultimate responsibility for the accuracy, authenticity, and timely collection and reporting of all clinical, safety, and laboratory data entered on the CRFs and any other data collection forms.

11.3 Data Validation

Validation checks programmed within RedCAP, as well as supplemental validation performed via review of the downloaded data, will be applied to the data in order to ensure accurate, consistent, and reliable data. Data identified as erroneous, or data that are missing, will be corrected.

The paper CRFs must be reviewed and signed by the Investigator.

12 INVESTIGATOR REQUIREMENTS AND QUALITY CONTROL

12.1 Ethical Conduct of the Study

The Investigator agrees to adhere to the instructions and procedures that are described in the protocol and to conduct the study in accordance with the CFRs (21 CFR § 11, 50, 54, 56, and 312 Subpart D), which originate from the ethical principles laid down in the current revision of the Declaration of Helsinki, Good Clinical Practice (GCP),^{26,27} and the policies and procedures as outlined by the ethical requirements for IRB review and informed consent form.

The Investigator agrees to allow inspection by the FDA or other appropriate regulatory authorities as needed.

The Investigator will ensure proper implementation and conduct of the trial, including those studyrelated duties that are delegated to other appropriately qualified individuals. The Investigator will ensure that study staff cooperates with monitoring and audits and will demonstrate due diligence in recruiting and screening study participants.

12.2 Institutional Review Board (IRB)

Before initiation of the study, the Investigator will obtain approval or favorable opinion of the research protocol, informed consent form, and any advertisement for participant recruitment from an IRB complying with the provisions specified in 21 CFR §56 and applicable pertinent state and federal requirements of each participating location including International Conference on Harmonization (ICH) and GCP guidelines.

Institutional review boards must be constituted according to the applicable laws. It is the responsibility of each investigational site to submit the protocol, Investigators' Brochure, participant

informed consent, participant recruitment materials (if applicable), and other documentation as required by the IRB to their IRB for review and approval.

The study site will adhere to all requirements stipulated by their respective IRB. This includes notification to the IRB regarding: protocol amendments, updates to the participant informed consent, recruitment materials intended for viewing by participants, serious and unexpected AEs, reports and updates regarding the ongoing review of the trial at intervals specified by the respective IRB, and submission of final summaries to IRB.

The Investigator will promptly inform his/her IRB of all unexpected SAEs considered possibly related to the treatment or other critical safety information reported by the clinical site.

